5.6 DEFINITION OF END OF TRIAL

The End of Trial will be the date of the last subject's end-of-treatment visit.

5.7 PROTOCOL DEVIATIONS, PATIENT DISCONTINUATION, AND STUDY TERMINATION CRITERIA

5.7.1 Protocol Violations/Deviations

Protocol violations are defined as a departure from the protocol that affects patient safety or benefit potential, or confounds assessments of safety or clinical activity. A protocol deviation is a departure from the protocol that does not meet the above criteria. Protocol violations or deviations may be grouped into the following classes:

- Enrollment criteria
- Study activities
- Noncompliance to dose or schedule, including dose calculations, administration, and interruption; reduction; or discontinuation criteria
- Clinical trial handling including storage and accountability
- Informed consent and ethical issues

Protocol violations/deviations will be reported as per IRB policy.

5.7.2 Patient Withdrawal

Inform patients that they may withdraw from this clinical study at any time without jeopardizing their relationship with their health care providers. Follow up details are provided in Section 5.7.5.

5.7.3 Investigator Discontinuation of Patient

The Investigator may exercise medical judgment to discontinue a patient's treatment with tosedostat because of clinically significant changes in any clinical or laboratory parameter. Follow up details are provided in Section 5.7.5.

5.7.4 Criteria for Protocol-Defined Required Discontinuation of Treatment

- Discontinue treatment with tosedostat if patients experience any of the following:
- Do not achieve CR, PR, hematologic improvement, or bone marrow remission after four cycles of treatment with tosedostat alone or 4 cycles of azacitidine if azacitidine is added to tosedostat.
- Experience disease progression
- Develop an intercurrent illness that prevents further treatment with tosedostat
- Develop unacceptable/intolerable AE(s)
- Withdraw from the clinical study
- Become pregnant
- Receive other systemic cancer therapy or protocol-prohibited medications
- Have general or specific changes that render the patient unsuitable for further treatment with tosedostat, in the judgment of the Investigator

5.7.5 Follow Up at Treatment Discontinuation or Early Withdrawal

Patients treated with tosedostat should have an End-of-Treatment Visit within 7 days of last dose of tosedostat and before the start of a new cancer therapy. End-of-Treatment Visit assessments are listed in Section 5.3.

5.7.6 Study Termination

The Investigator has the right to terminate this clinical study at any time. Reasons for terminating the clinical study or a clinical site's participation include, but are not limited to, the following:

- The incidence or severity of an adverse reaction in this or other studies, indicating a potential health hazard to patients
- Unsatisfactory patient enrollment
- Inaccurate or incomplete data recording
- Site personnel noncompliance to study procedures

Request from regulatory body such as the FDA or IRB

5.8 Correlative Studies

Samples will be collected for studies related to MDS. The samples consist of peripheral blood and bone marrow aspirate. Approximately 10 - 30mL of bone marrow aspirate and up to 20mL of peripheral blood will be collected at the following time points:

- Screening
- Cycle 1 Day 15 (peripheral blood only)
- End of C2
- Any clinically relevant points thereafter as indicated to be safe by the Investigator

The collection of these samples occurs during standard of care timepoints. Patients will not undergo a separate procedure for the collection of these samples. Samples will also be stored for possible future studies. The appropriate future research language and genetic testing language is included in the consent form for subject notification and information.

Samples will be stored indefinitely unless the patient provides a written request for destruction of their specimens.

6 STUDY TREATMENTS

6.1 IDENTITY OF INVESTIGATIONAL PRODUCT(S)

Basic information about the study treatments is provided in Table 4.

Table 4: Study Treatments

Test Product:	CHR-2797
Trade Name	Tosedostat
Manufacturer	Patheon UK Ltd.
Dose	120 mg daily
Route of administration	Oral
Formulation	Hard gelatin capsules, in blister packs
Capsule strengths	60 mg

Tosedostat will be provided by CTI BioPharma Corp. in bottles of 30, 60 mg capsules. A 120 mg once daily dose will require the subject to take 2 capsules per day. Shelf life details will be clearly printed on the packaging labels and accompanying documentation. The product should be stored below 30°C (86°F), protected from moisture and light. Do not freeze.

6.2 ADMINISTRATION AND TIMING OF DOSE

The dose regimens of tosedostat will be 120 mg once daily.

The dose of tosedostat should be taken orally with a glass of water after food, preferably in the morning at about the same time every day to ensure an even dose interval.

6.3 ADDITION OF AZACITIDINE FOR NON-RESPONSE

If at end of two cycles of tosedostat, patient does not have response as defined as above, the investigator has discretion of adding azacitidine in addition to tosedostat. Dosing will be standard dosing (azacitidine 75mg/m²), either subcutaneously or intravenously, for 5 continuous days every 28 days.

6.4 MONITORING OF CARDIAC FUNCTION

In view of possible cardiotoxic potential of tosedostat, cardiac monitoring includes routine troponin I, BNP, EKG, and transthoracic echocardiogram every cycle. If a patient has been off tosedostat for more than 2 weeks, then an additional transthoracic echocardiogram will be done prior to starting subsequent cycle (day 1 of the next cycle). Clinically significant cardiaovascular events will be assessed by the investigator, and investigator may reduce or hold dose of tosedostat until cardiovacular studies return back to baseline.

6.5 DOSE MODIFICATIONS AND INTERRUPTIONS

The Investigator may temporarily discontinue dosing of tosedostat for safety reasons, for example if the Investigator considers that an AE is related to tosedostat. The Investigator should document the reasons for discontinuation, and should contact the Medical Monitor to discuss the case and possible options. In addition, the Investigator may reduce the dose of tosedostat to 60 mg once daily for safety reasons for which the Investigator considers temporary or permanent discontinuation is unnecessary.

Throughout the clinical study, safety is assessed for all patients through laboratory evaluations, vital signs, physical examinations, ECGs, echocardiogram, and the incidence and severity of AEs/SAEs. Doses may be reduced or held based on the toxicity of drug-related hematologic and non-hematologic toxicities that occur during the preceding cycle.

There will be no dose adjustments based on hematologic parameters EXCEPT for grade 4 hematologic toxicities. Dose adjustments pertaining to non-hematologic and hematologic toxicities should be performed as follows:

DRUG-RELATED AE	ACTION
CTCAE Grade 1	No adjustments needed
CTCAE Grade 2	Investigator's option to reduce or hold dose
CTCAE Grade 3 ^a	
• If non-hematologic toxicity, withhold dose until recovery to baseline. If it persists for more than 14 days, Investigator will determine if patient will discontinue treatment.• If hematologic toxicity, no dose adjustments will be made.
CTCAE Grade 4	
• If hematologic toxicity, Investigator will determine if the patient may continue on study with appropriate dose reduction.

- If non-hematologic toxicity, patient will discontinue treatment.

a Excluding nausea, vomiting, or diarrhea controlled with antiemetic or antidiarrheal therapy; alopecia; Grade ≥ 3 mucositis lasting < 5 days; Grade ≥ 3 AST or ALT elevation lasting < 7 days; and infection/febrile neutropenia controlled with antibiotics.

The reasons for any dose adjustments for any patient should be documented in the patient's source record.

Adverse events to be excluded from consideration for dose adjustments include:

- Alopecia
- Grade ≥ 3 mucositis lasting < 5 days
- Grade ≥ 3 aspartate aminotransferase (AST) or alanine aminotransferase (ALT) elevation lasting < 7 days
- Infection/febrile neutropenia controlled with antibiotic therapy
- Grade 4 hematologic AE: anemia, neutropenia, or thrombocytopenia persisting after cycle 2 in the presence of residual MDS
- Other grade 3 or higher non-hematologic toxicity that are clearly and incontrovertibly due to extraneous causes
- Grade 3 or greater nausea, diarrhea, or vomiting that is managed with the use of medical intervention

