Patients with a documented response of CR, PR, hematologic improvement or stable disease at the end of Cycle 2 may be eligible to continue treatment indefinitely with tosedostat, at the discretion of the Investigator.. Study visits during Cycles 2+ have a 2-day window. Patients must have returned to at least baseline hematological parameters at the start of each cycles unless investigator deems cytopenias are secondary to underlying disease, and all drug-related non-hematological toxicities must have resolved to < grade 2.

5.2.2.1 *Day 1*

- Recording of any changes to medical history since the Screening Visit

- Recording of baseline signs and symptoms
- Physical examination, including assessment of extramedullary disease
- Assessment of ECOG performance status
- Vital signs, including body temperature (°C), pulse rate and systolic and diastolic blood pressures, weight (kg), and body surface area
- Collect blood samples for hematology, troponin I, b type natriuretic peptide, coagulation, and blood chemistry (blood samples may be omitted if obtained within 7 days)
- Collect urinalysis (may be omitted if obtained within 7 days)
- Perform 12-lead ECG
- Transthoracic echocardiogram, only if patient has been off of tosedostat for more than 2 weeks since prior cycle
- Recording of concomitant medications and significant non-drug therapies including blood product transfusions
- Assess and record of AEs
- Examination of subject treatment diary and return of unused tosedostat
- Dispense tosedostat

5.2.2.2 *Days 8, 15, 22*

- Physical examination, including assessment of extramedullary disease
- Vital signs, including body temperature (°C), pulse rate and systolic and diastolic blood pressures, weight, and body surface area
- Collect blood samples for hematology, chemistry, troponin I, b-type natriuretic peptide
- Perform 12-lead ECG
- Recording of concomitant medications and significant non-drug therapies including blood product transfusions
- Recording of AEs

5.2.2.3 *Days 28*

- Physical examination, including assessment of extramedullary disease
- Vital signs, including body temperature (°C), pulse rate and systolic and diastolic blood pressures, weight, and body surface area
- Collect blood samples for hematology, chemistry, troponin I, b-type natriuretic peptide
- Perform 12-lead ECG
- Transthoracic echocardiogram
- Recording of concomitant medications and significant non-drug therapies including blood product transfusions
- Recording of AEs

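### Section 6.5 gives conflicting instructions for hematologic grade 2 toxicity and for a short list of grade 4 non-hematologic events

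*Combined protocol and SAP*

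**What the plan says.** All of the following is in Section 6.5 unless stated otherwise.

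- A general paragraph permits changes for either type of toxicity, with no grade limit: "Doses may be reduced or held based on the toxicity of drug-related hematologic and non-hematologic toxicities that occur during the preceding cycle".
- The next paragraph restricts this: "There will be no dose adjustments based on hematologic parameters EXCEPT for grade 4 hematologic toxicities". It then introduces the table: "Dose adjustments pertaining to non-hematologic and hematologic toxicities should be performed as follows".
- The grade 2 row of the table reads "Investigator's option to reduce or hold dose" and does not separate hematologic from non-hematologic events. The grade 3 and grade 4 rows do separate them. For hematologic events, grade 3 allows no adjustment and grade 4 leaves continuation at a reduced dose to the investigator. For non-hematologic events at grade 4 the instruction is: "If non-hematologic toxicity, patient will discontinue treatment".
- Footnote a exempts certain events. Its marker stands on the grade 3 row only, although for mucositis and AST/ALT its wording covers grade 3 and above.
- A list after the table names events left out when dose adjustments are considered. It includes "Grade ≥ 3 aspartate aminotransferase (AST) or alanine aminotransferase (ALT) elevation lasting < 7 days", mucositis of grade 3 or above lasting under 5 days, infection or febrile neutropenia controlled with antibiotics (no grade given), and nausea, diarrhea or vomiting of grade 3 or above that is medically managed.
- Section 5.2.2 adds a start-of-cycle condition: "Patients must have returned to at least baseline hematological parameters at the start of each cycles". It makes an exception where the investigator attributes the cytopenias to the underlying disease.

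**The concern.** The same drug-related event can fall under two instructions in one section. If so, time on drug, dose received and the reason recorded for stopping depend on which sentence the treating physician relies on, and the safety tables inherit that variation. Section 5.7.1 counts departures from the interruption, reduction and discontinuation criteria as protocol violations or deviations. Where two criteria apply to one event, compliance cannot be judged.

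Liver events are among those affected. Section 1.1.4.2 reports a grade 3 ALT rise as a dose-limiting toxicity at 130 mg, and Section 1.1.4.3 names acute hepatitis among the fatal events possibly related to tosedostat. This is background on why clear transaminase rules matter. It does not show that a disputed case has occurred.

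**Working it through.** No arithmetic applies. The check sets the Section 6.5 text, table, footnote a and exclusion list side by side, by grade and type of event, for drug-related events (the scope of the table).

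**Hematologic events**
- Grade 1: the restricting sentence allows no adjustment and the table says none is needed. They agree.
- Grade 2: the restricting sentence allows none, while the table gives an option to reduce or hold. They conflict. The row cannot simply be assumed to mean non-hematologic events, because the table is introduced as covering both types and the rows for grades 3 and 4 mark the split where they intend one. Read as written, the table allows a change at hematologic grade 2 and none at grade 3.
- Grade 3: the restricting sentence and the table both allow none. They agree. Only the earlier general paragraph, which has no grade limit, differs.
- Grade 4: the sentence and the table both allow a change. The list removes grade 4 cytopenias that persist after cycle 2 with residual MDS, which reads as an ordinary exception.

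**Non-hematologic events**
- Grade 3: the table withholds the dose. Footnote a and the list exempt much the same events, apart from slightly different wording for gastrointestinal events. They broadly agree.
- Grade 4, event not on the list: the table requires discontinuation and nothing contradicts it.
- Grade 4, event on the list: the table requires discontinuation, while the list removes the event from dose-adjustment consideration. A threshold of grade 3 or above includes grade 4, and the infection item has no grade limit. They conflict unless the list overrides the row, which the text does not say.

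Two features keep the second conflict open. First, the marker for footnote a is absent from the grade 4 row. Second, the list speaks of dose adjustments, and nothing states whether permanent discontinuation is one. There is also a timing problem: whether an AST/ALT elevation will last under 7 days, or mucositis under 5, is unknown on the day the grade 4 row first applies.

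The list item on toxicity from extraneous causes is not a conflict, because the table covers only drug-related events.

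**Start of cycle.** Take a drug-related grade 3 cytopenia that has not returned to baseline when a cycle is due. Section 5.2.2 does not let the cycle start, and its exception for disease-related cytopenia does not reach a drug-related one. The Section 6.5 table says no adjustment. Section 3.1 makes dosing continuous, so a delayed cycle works as a hold. The two rules do not fit together for this case.

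**The case against.** The strongest reply is that Section 6.5 can be read as rules with exceptions.

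- *Hematologic grade 2.* The row is permissive, and the sentence just above the table is specific to hematologic parameters, so it may limit the general row. Not adjusting satisfies both. This stands in part: the passages do not compel opposite actions. But an investigator who uses the option follows the table and departs from the sentence.
- *Grade 4 non-hematologic.* The list reaches grade 4 by its own wording, as does the text of footnote a for mucositis and AST/ALT, so the list may be a general exception. This is plausible and may be what was intended. The documents do not settle it, for the reasons given in the working.
- *Section 5.2.2.* It governs starting a cycle, not dose changes for adverse events, and it carries an exception. That is fair, and it is why this is a related misfit and not a third contradiction.
- *Practice.* The trial has a single center, Section 6.5 has the investigator contact the Medical Monitor when dosing is temporarily discontinued, and Section 5.7.4 already requires stopping for unacceptable events. This limits the number of interpreters but does not supply the missing rule. Section 5.7.4 names no grade.
- *Safety history.* The ALT dose-limiting toxicity was grade 3, where the passages agree for short elevations, and the duration of the hepatitis event is not given. Neither illustrates a short grade 4 rise. This stands.

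A reader might go further and infer that all hematologic toxicity below grade 4, or every grade 4 non-hematologic event, is affected. The documents do not support that: hematologic grades 1 and 3 agree with the restricting sentence, and unlisted grade 4 events have one clear instruction.

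**Conclusion.** The point holds in two places: hematologic grade 2, where the text and table differ, and drug-related grade 4 non-hematologic events on the exclusion list, where the table and list differ. The Section 5.2.2 condition should be reconciled with them. This assumes that the unqualified grade 2 row covers both types of toxicity, as the table's introduction says, and that a threshold of grade 3 or above includes grade 4.

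The number of patients affected cannot be derived. A reader might scale the OPAL 120 mg rates in Table 2 to this trial: grade 3-4 thrombocytopenia 8/38 × 80 = 16.8, about 17 patients, and grade 3-4 febrile neutropenia 11/38 × 80 = 23.2, about 23 patients. These are not counts of disputed cases. The table pools grades 3 and 4, gives no attribution to drug, and comes from patients with AML. The thrombocytopenia figure contains no grade 2 events, which is where the hematologic conflict lies. For febrile neutropenia, only a drug-related grade 4 event controlled with antibiotics and classed as non-hematologic could be in dispute.

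No effect on the overall survival endpoint is shown. The consequence is inconsistent conduct and unclear compliance, which is enough to justify correcting the text.

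**What to change.** Reconcile the Section 6.5 text (including the general paragraph), table, footnote a, exclusion list and the Section 5.2.2 start-of-cycle rule so that each grade and type of event leads to one action. In particular, state:

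- whether the grade 2 row applies to hematologic events;
- whether the exclusion list and footnote a apply to the grade 4 row;
- whether discontinuation counts as a dose adjustment;
- how the duration-based exclusions operate before the duration is known;
- how the start-of-cycle condition relates to the grade 3 hematologic row.

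The clinical team decides which action is intended; this review takes no position on that. The same edit should check Section 6.7, which allows dosing changes only under Section 6.3 (now the azacitidine section), although the modification rules are in Section 6.5.

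The cost is a protocol wording amendment. The sample size, endpoints and analysis do not change.

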6.6 PRIOR AND CONCOMITANT TREATMENTS

Medications taken by, or administered to, the subject within 28 days prior to first dose of tosedostat, or up to 28 days after the final dose of tosedostat, should be recorded. The entry should include the generic name, dose regimen, route, indication, and dates of use.

6.6.1 Best Supportive Care

All subjects should receive best supportive care including, but not limited to, transfusions of red cells (with iron chelation therapy as needed), platelets, and medication for the prevention and treatment of infections and hyperuricaemia. These are all given at the discretion of the Investigator and should be fully documented in the eCRF. Best Supportive Care should be recorded for treatments given in the 28 days prior to first dose of tosedostat, or up to 28 days after the final dose of tosedostat.

6.6.2 Allowed Medications

The following medications may be used within the recommendations of nationally applicable marketing approvals and the following limits:

- Anticoagulant Therapy: subjects who are taking warfarin (or equivalent) may participate in this study; however, it is recommended that prothrombin time (PT) be monitored carefully at least twice per week for the first month, followed by the pre-study level of monitoring if the international normalized ratio is stable. Subcutaneous heparin is permitted

- Colony Stimulating Factors: the routine use of granulocyte colony stimulating factors (GCSFs or GM-CSFs) is permitted for the treatment of neutropenic sepsis during this study. Subjects should not receive G-CSFs prophylactically in general.
- When use of concomitant medications with QT-prolonging potential is necessary, ECG must be repeated 4 hours post-dose on Day 1 (+1 day), on Day 3 (± 1 day), and on Day 7 (± 1 day), and as clinically indicated, relative to start of agent with QT-prolonging potential. QTc will be calculated using the Fridericia formula.

6.6.3 Excluded Medications

Immunotherapy, hormonal cancer therapy, high-dose corticosteroids (other than topical, intra-articular, inhaled, short courses for the prevention of hypersensitivity, for example during blood product transfusions, or other locally administered steroids), radiation therapy (except small field radiotherapy with palliative intent) or experimental medications are not permitted at any time after randomization.

6.6.4 Cytochrome P450 Interactions

Currently available *in vitro* data suggest that tosedostat may be a moderate inhibitor of selected catalytic activities of CYP4503A4. Therefore, it may participate in, or contribute to, inhibitory drug-drug interactions *in vivo*, which are mediated by cytochrome P4503A4. Drugs that are known to be substrates for CYP4503A4 should be used with caution, examples of which include acetaminophen, carbamazepine, cyclosporin, digitoxin, diazepam, erythromycin, felodipine, fluoxetine, nifedipine, quinidine, saquinavir, terfenadine, triazolam, verapamil, and warfarin.

It is not expected, however, that tosedostat will reach sufficiently high, prolonged concentrations to significantly impact upon the metabolism of such drugs. Tosedostat has little effect on the enzyme activities of CYP1A2, CYP2C9, CYP2C19, CYP2D6, and CYP2E1.

6.7 TREATMENT COMPLIANCE

The prescribed dosage, timing, and mode of administration may not be changed, except as stipulated in Section 6.3. Any departures from the intended regimen must be documented. Overdoses should be reported to a CTI BioPharma Corp. representative or designee. The clinical manifestation (if any) of an overdose should be reported as an AE or SAE, as appropriate.

Subjects will be issued with a diary in which they should record study drug taken or omitted. Reasons for omission should be recorded. At the end of each month during the study, prior to dispensing further study medication, the treatment diary will be reviewed, previously dispensed study medication will be retrieved by the Investigator and compliance assessed. Subjects exhibiting poor compliance as assessed by capsule counts should be counselled on the importance of good compliance to the study dosing regimen.

Non-compliance is defined as taking less than 80% of study medication during any evaluation

period (visit to visit). Protocol permitted dose discontinuations will not be counted towards this percentage. Subjects exhibiting poor compliance may be withdrawn from the study. A discussion between the Investigator and the Medical Monitor must occur before this happens.

